**Phase 1 study design:** Consented participants will have clinic BP measured at the screening visit and will enter a two-week usual diet period, during which antihypertensive medications, with the exception of calcium channel blockers, will be weaned off under [name] supervision and with guidance from daily home BP monitoring. During this time period, the participant will consume their usual diet. Potential subjects with ontreatment, resting, average systolic BP of > 160 mmHg at the screening visit will be excluded from further

participation, as will those with symptomatic hypertension or systolic BP of > 180 mmHg on more than one occasion during the ad-lib dietary period.

Following the usual diet period and the week 2 visit, participants will consume the DASH/SRD diet for 14 days each. This time period is sufficient to demonstrate changes in BP and arterial stiffness, which peak at 2 weeks after dietary sodium modification (Gates et al. 2004). In addition to in-clinic BP measurement, 24-hour ambulatory BP will be obtained at the end of each dietary sequence. We expect that the DASH/SRD will reduce BP across the cohort, but differentially on an individual basis (Sacks et al. 2001).

The salt-sensitive vs. salt-resistant phenotype will be defined as a change in 24-hour mean BP of ≥8 mmHg between control and DASH/SRD dietary segments (Castiglioni et al. 2011). Based on previous studies in patients with HTN, we expect that 30-50% of participants will be classified as salt-sensitive (Elijovich et al. 2016). The 24-hour ambulatory BP monitoring and 24-hour urinary collections will be used to provide an alternate definition of salt-sensitivity. Specifically, the quantitative Sodium Sensitivity Index will be calculated as the change in 24-hour mean BP divided by the change in 24-hour urinary sodium excretion between DASH/SRD and control diet periods (Castiglioni et al. 2011).

The *Phase 1* primary outcome is the cfPWV compared at the end of usual diet and DASH/SRD. This parameter was chosen because of its association with incident HF in community-dwelling elderly (Tsao et al. 2015) and its high sensitivity and specificity for HF in older adults with unexplained exertional dyspnea (Weber et al. 2013). Key secondary outcomes include ventricular diastolic function (k; ventricular stiffness) and systolic function (global longitudinal ventricular strain) and left atrial reservoir function (left atrial strain).

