An intention-to-treat approach will be used to analyze endpoints, including all randomized participants. Multiple imputation will be used for missing data, which assumes that outcome data are missing at random (i.e., where other variables from the study can account for differences in the primary outcome for observed and missing subjects) (Little et al. 2012). A linear mixed effects model (Verbeke et al. 2000, Diggle et al. 2013) will be used to assess the effect of intervention on the change in cfPWV, with fixed-effect terms for sequence, study period, dietary intervention, and adjusting for baseline cfPWV and other potential confounders, e.g. age, race, body mass index, diabetes status, and renal function. A random-effect term will be included to account for the correlated measurements for each subject. Tests to compare diet will be based on Wald and chi-squared tests based on maximum likelihood or restricted maximum likelihood methods. Alternative covariance structures (other than compound symmetry) will be explored and model fit will be examined using the Akaike Information Criteria (Holford 2004). This approach will also be used for the key secondary endpoints (ventricular diastolic stiffness k and global longitudinal ventricular strain) and other cardiovascular parameters (e.g. E/e' ratio). For binary secondary outcomes (e.g. serious adverse events) a similar mixed model approach will be employed (Ezzet et al. 1992). To test whether improvements in the primary and key secondary endpoints are greater in salt-sensitive than in salt-resistant subjects, interaction will be assessed via the linear mixed model described above, with a fixed-effect term for salt-sensitivity phenotype.

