Study Phase 2: Assess the efficacy of motivational interviewing plus the WHEELS-I program vs. motivational interviewing alone in promoting adoption of the DASH/SRD. Determine the effects of DASH/SRD adoption over a 6-month period on structural cardiovascular HFpEF risk factors in salt sensitive vs. salt-resistant veterans.

*Introduction:* Structural correlates of HFpEF include left ventricular hypertrophy, which strongly predicts HF onset in older adults, left atrial enlargement, which reflects chronically elevated ventricular filling pressures, and stiff central arteries. No previous studies in participants with HTN and metabolic syndrome have examined the relationship between the salt-sensitive phenotype and these HFpEF risk factors after long-term dietary

modification. Current guidelines recommend the DASH/SRD to prevent cardiovascular disease in hypertensives with metabolic syndrome, but adherence to this dietary pattern is declining nationwide. Our working hypotheses are that: 1) When compared to motivational interviewing alone, the addition of the Women's and Men's Hypertension Experiences and Emerging Lifestyles Intervention (WHEELS-I) program, an electronically-delivered tailored messaging intervention, will improve adoption of the DASH/SRD over a six month period, and 2) sustained adoption of the DASH/SRD over 6 months will produce greater improvement in structural cardiovascular HFpEF risk factors in salt-sensitive than salt-resistant subjects, with measures including left ventricular mass index (LVMI, primary outcome), left atrial volume index (LAVI), cfPWV, and BP.

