Sample size and power: The sample size for *Phase 2* is set by the goals of *Aim 1* and influenced by drop-out during the 6 months of the interventions to promote DASH/SRD adoption. We assume that an additional 10% of subjects will drop out during *Phase 2* and that the dropout rate will be equal in salt-sensitive and salt-resistant participants, resulting in 90 subjects with evaluable data. The primary outcome of *Aim 2* of this proposal is the DASH/SRD concordance score from the Block Food Frequency Questionnaire in participants assigned to the WHEELS-I group vs. motivational interviewing alone. Based on national survey data and our preliminary work, we expect the mean baseline (Week 2 visit) dietary score to be 2.5±1.5. A sample size of 90 provides >80% power to detect an intra-group change of 0.6 between baseline and the end of study, based on paired t-testing two-sided Type I error of 5%. This sample size provides >80% power to detect a differential between group change in dietary score of 0.9, based on a two-sample t test and two-sided Type I error of 5%.

With regard to cardiovascular parameters, a sample size of 90 provides >80% power to detect an effect size of 0.6 in the primary endpoint of change from baseline to month 6 in LVMI between salt-sensitive vs. salt-resistant subjects (assuming a 50:50 split of salt sensitive vs. salt-resistant participants), with a two-sided Type I error of

5%. This between-groups comparison is based on a two-sample t test. Conservatively assuming that the standard deviation of the change in LVMI between baseline and 6 months ranges between 4 to 7 g/m2.7 (Blumenthal et al. 2010), this effect size translates to mean group differences of 2.4 to 4.2 g/m2.7. This would represent a 5-10% decrease in LVMI from baseline in salt-sensitive subjects (vs. no change in salt-resistant), similar to that in previous studies of dietary sodium restriction (Jula et al. 1994, Liebson et al. 1995).

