Analysis plan: Paired and 2-sample t-testing will be used to analyze changes in DASH/SRD concordance score as above, as well as changes in 24-hour urinary sodium excretion. The methods to analyze cardiovascular changes in *Aim 2* will be identical to those used in the comparison of salt sensitivity phenotypes in *Aim 1* (see above). Important covariates in the models to compare changes in cardiovascular parameters by salt-sensitive/resistant phenotype will be the degree of DASH/SRD concordance and changes in 24-hour BP.

Potential problems/alternative approaches: While motivational interviewing and the WHEELS-I program have been effective in our preliminary studies, we expect individual variance in DASH/SRD adoption. The primary analysis will be an intent-to-treat framework; secondary analyses will test interaction with the level of DASH/SRD adoption. (Mellen et al. 2008) We expect that participants who successfully adopt DASH/SRD will substantially change their eating habits. The WHEELS-I program does not target weight loss, but since sodium intake correlates with caloric intake (Guenther et al. 2013) it is possible that some veterans may lose weight during *Phase 2*. We do not a *priori* expect differential weight loss in salt-sensitive and salt-resistant subjects. However, since cfPWV and LVMI can both be reduced through weight loss, we will perform analyses adjusted for *Phase 2* weight changes (Blumenthal et al. 2010). If the proportions of salt-sensitive and salt-resistant subjects are not equal (say 60%:40%), we would retain >80% power to detect effect size of 0.61.

Specific Aim 3 (spans Study Phases 1 and 2): Determine effects of DASH/SRD feeding and longer-term adoption on microvascular function, and assess the relationship between endothelial glycocalyx integrity/sodium buffering and cardiovascular response to DASH/SRD.

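### The protocol adjusts the Phase 2 salt-sensitivity comparison for change in 24-hour BP, so the adjusted coefficient is not the total difference that was hypothesised and powered

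*Protocol*

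**What the plan says.** The protocol's Study Phase 2 introduction hypothesises that sustained adoption of the diet "will produce greater improvement in structural cardiovascular HFpEF risk factors in salt-sensitive than salt-resistant subjects". It attaches no condition about BP. Phase 2 study design makes change in LVMI from the Week 2 visit to 6 months the primary cardiovascular outcome. Carotid-femoral pulse wave velocity (cfPWV), left atrial volume index and 24-hour mean BP are key secondary outcomes. Phase 2 Sample size and power gives more than 80% power for 0.6 SD with 90 participants split equally, and states: "This between-groups comparison is based on a two-sample t test".

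The Phase 2 Analysis plan says the cardiovascular methods "will be identical to those used in the comparison of salt sensitivity phenotypes in" Aim 1. The Aim 1 model is a linear mixed model "adjusting for baseline cfPWV and other potential confounders, e.g. age, race, body mass index, diabetes status, and renal function". The plan then adds that the important covariates in models to "compare changes in cardiovascular parameters by salt-sensitive/resistant phenotype will be the degree of DASH/SRD concordance and changes in 24-hour BP".

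The next section, Potential problems/alternative approaches, makes the primary analysis intent-to-treat and says that "secondary analyses will test interaction with the level of DASH/SRD adoption". It treats weight separately: "since cfPWV and LVMI can both be reduced through weight loss, we will perform analyses adjusted for" weight change in Phase 2. The BP-adjusted models carry no primary or secondary label.

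Phase 1 study design says the phenotype is "defined as a change in 24-hour mean BP of ≥8 mmHg between control and DASH/SRD dietary segments". In the SAP, salt-sensitivity groups are compared for Phase 1 only. Phase 2 LVMI and pulse wave velocity are compared between WHEELS and non-WHEELS arms by linear regression adjusted for baseline value.

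**The concern.** A covariate measured after baseline that may carry part of the effect changes what the group coefficient means. Here there are three links between the covariate and the comparison.

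- **Overlap with the grouping.** Phenotype is the Week 2 to Week 4 change in 24-hour BP. If the covariate also starts at Week 2, as LVMI change does, the two share one reading. Groups can then differ on the covariate through that reading alone.
- **Covariate as outcome.** 24-hour mean BP is among the Phase 2 outcomes compared by phenotype. The covariate sentence makes no exception for it. Over the same interval, the outcome would be regressed on itself and nothing would be left to estimate.
- **Mixed content.** Apart from calcium channel blockers, antihypertensives are weaned before the Week 2 visit, and prior therapy is resumed in Phase 2. BP change therefore reflects drugs as well as diet, so the adjusted coefficient is not a clean BP-independent effect either.

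If the BP-adjusted model were read as the main test, a true LVMI or cfPWV difference acting partly through BP would be reported as smaller than it is. The plan also does not say over which visits BP change is taken.

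**Working it through.** **Plan's own figure.** Inputs from Phase 2 Sample size and power: 0.6 SD, 45 vs 45, two-sided 5%, two-sample t test. Noncentrality = 0.6/√(1/45 + 1/45) = 2.85 on 88 df, giving power 80.4%. The stated figure reproduces, as does its translation: 0.6 × 4 = 2.4 and 0.6 × 7 = 4.2 g/m^2.7. At 27 vs 63 (30% salt-sensitive, the low end of the protocol's 30–50%), power is 73.2%. All these figures belong to the unadjusted total difference.

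**Adding BP change.** Let g be the group gap in BP change (within-group SD units), ρ the within-group correlation of BP change with LVMI change, and p the salt-sensitive fraction. Then:

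- coefficient = 0.6 − ρg
- SE = √[(1 − ρ²)(1/n1 + 1/n2)(1 + p(1 − p)g²)], on 87 df

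The documents give neither ρ nor g, so everything below is assumption.

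*A. BP change unrelated to phenotype (g = 0).* The coefficient stays 0.60. With ρ = 0.2, 0.3 or 0.5, power is 82%, 84% or 90%: a small gain.

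*B. Groups differ on BP change, but it is unrelated to LVMI change (ρ = 0).* The coefficient stays 0.60. With g = 0.36, 0.52 or 0.87, power is 79%, 78% or 73%: some precision lost, no bias.

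*C. Shared Week 2 reading.* Assume equal variances, Week 2–Week 4 correlation r24, and correlation 0.5 of each with Month 6. The Week 2–Week 4 and Week 2–Month 6 changes then correlate 0.5 × √[(1 − r24)/(1 − 0.5)]. With a normal median split and ρ = 0.3:

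| r24 | correlation of changes | g | coefficient | power, 45/45 |
|---|---|---|---|---|
| 0.5 | 0.500 | 0.87 | 0.6 − 0.3 × 0.87 = 0.34 | 33% |
| 0.8 | 0.316 | 0.52 | 0.44 | 56% |
| 0.9 | 0.224 | 0.36 | 0.49 | 66% |

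A simulation (6,000 runs per row) gave coefficients 0.340, 0.449 and 0.491 and power 33%, 57% and 65%. At 27 vs 63 the coefficients are 0.33, 0.44 and 0.49, with power 28%, 48% and 58%. The inputs matter: at r24 = 0.8, setting ρ and the Month 6 correlation both to 0.2 gives 0.52 SD and 68%. A higher Month 6 correlation moves the result the other way.

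*D. Part of the difference runs through BP.* A share s requires g = 0.6s/ρ. Only cells with g no larger than the 0.87 seen in C are kept:

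- s = 25%: coefficient 0.45; ρ = 0.2, 0.3, 0.5 needs g = 0.75, 0.50, 0.30; power 52%, 57%, 67%.
- s = 50%: coefficient 0.30; ρ = 0.5 needs g = 0.60; power 34%.

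Lower powers can be generated, but the lowest need gaps of 1.5 to 2.25 SD (for example 0.5 × 0.6/0.2 = 1.5), so they are set aside.

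**If BP change means the Phase 1 change.** The covariate is then the variable that was dichotomised to form the groups. Under a normal median split its correlation with phenotype is √(2/π) = 0.80, and the variance inflation is 1/(1 − 2/π) = 2.75.

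None of these figures includes baseline LVMI or the Aim 1 covariates, so they illustrate direction and do not give the power of either full model.

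**The case against.** The strongest objection is that no current plan contains this model. The SAP is written in the past tense, compares WHEELS arms in Phase 2 and adjusts for baseline value only. This stands, and it limits the point to the case where the phenotype comparison is still reported. It does not remove the point: the SAP does not say that comparison was dropped, and the protocol sentence is the only text that sets its Phase 2 covariates beyond the Aim 1 list.

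A second objection is that the protocol never calls the BP-adjusted model primary. The power section names an unadjusted t test, so the covariate sentence could describe explanatory models beside it. A reader might infer that BP adjustment is the declared primary test; the documents do not say so. Nor do they relegate it: the covariates are stated as a rule for the phenotype models, and intent-to-treat does not settle covariates.

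A third objection is that the size is indeterminate, and this also stands. A reader might infer that the planned power is wrong or falls to single figures. The 80% is correct for the comparison it describes, and the very low values rest on implausible gaps.

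Finally, leaving BP change out is not free of bias. Phenotype is not randomised, and if resumption of therapy differs by phenotype, the comparison without BP change can carry drug-related LVMI change. That is a fair limitation of the proposed primary model.

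A reader might also class diet concordance as a mediator. It is post-baseline, but the protocol calls it the measure of exposure and nothing shows it to be a mediator.

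**Conclusion.** The concern holds in a conditional form. If the Phase 2 phenotype comparison is reported as the protocol specifies, its BP-adjusted coefficient is a different quantity from the total difference hypothesised and powered, and the 24-hour BP outcome would be adjusted for itself. Both follow from the text and need no assumed numbers.

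The size for LVMI or cfPWV is not fixed by the documents. It runs from a small precision gain (82–90% power, coefficient 0.60 SD) when BP change is unrelated to phenotype, to attenuation when the Week 2 reading is shared. The latter gives 0.34 to 0.49 SD and 33% to 66% power under the correlations assumed in C. On the protocol's LVMI scale, 0.34 SD is 1.4 to 2.4 and 0.49 SD is 2.0 to 3.4 g/m^2.7, against the powered 2.4 to 4.2.

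The documents do not support saying that any Phase 2 result was actually BP-adjusted. This should be corrected; confidence in its practical weight is medium.

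**What to change.** First reconcile protocol and SAP on whether the phenotype comparison of LVMI is still reported. If it is not, say so, and the point closes. If it is, issue a dated, disclosed clarification that:

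1. makes the primary phenotype model the one adjusted for the baseline outcome value and a closed, prespecified list of any baseline covariates (the Aim 1 list is given only by example), without change in 24-hour BP;
2. labels the BP-change-adjusted and concordance-adjusted models as secondary and explanatory, and still reports them;
3. names the visits between which BP change is measured;
4. bars BP change as a covariate when 24-hour BP is the outcome.

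The variables are already in the protocol's schedule, so no new data are needed; phenotype models already run with BP change would be re-run. The cost is that differences between phenotypes in achieved diet or in resumed antihypertensive therapy stay in the primary estimate, which should be stated as a limitation. A small precision gain is also given up if BP change turns out unrelated to phenotype (80.4% against 82–90% in case A).

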[figure not shown]
Dietary Prevention of Heart Failure in Hypertensive Metabolic Syndrome

NCT03170375

May 31, 2025

Statistical Plan

The study was conducted in two phases. *Phase 1* evaluated the salt-sensitivity of blood pressure, with 2 weeks of ad-lib diet followed by 2 weeks of provided sodium-restricted Dietary Approaches to Stop Hypertension (DASH/SRD) meals, with outcomes assessed at 2 and 4 weeks of study participation. *Phase 2* evaluated the efficacy of motivational interviewing-based dietary counseling, with or without the Women's and men's Hypertension Experiences and Emerging LifestyleS (WHEELS) mobile application, with outcomes assessed from baseline to the end of the study. The study schematic is shown below, along with data collection and the flow of participants that were still actively participating at key timepoints.

The primary outcome of *Phase 1* was the change in carotid-femoral pulse wave velocity (PWV), with secondary outcome of the change in left ventricular global longitudinal strain by echocardiography, between week 2 and week 4 of study participation. Since *Phase 1* of the study occurred prior to randomization, the comparator groups are salt-sensitive and non salt-sensitive individuals, with blood pressure salt-sensitivity defined as a reduction in mean arterial pressure by 24-hour ambulatory monitoring in week 4 (DASH/SRD diet period) compared to week 2 (ad-lib diet period). *Phase 1* outcomes were analyzed using linear regression adjusted for baseline value.

Sample size was based on a 2-sequence, 2-period, 2-treatment crossover design for continuous endpoints (using paired t test for mean differences). We assumed a within-subject correlation of 0.70 for PWV measurements, based on our preliminary data and the literature and assumed a 10% dropout rate during *Phase 1* of our study. Under these assumptions and using a two-sided type I error rate of 5%, 100 subjects, 50 allocated to the DASH/SRD-control diet sequence and 50 allocated to the controlDASH/SRD diet sequence, provides >80% power to detect an effect

size (mean treatment difference/standard deviation) of 0.22 and >90% power to detect an effect size of 0.26. This sample size provides >80% power to detect an effect size of 0.5 in cfPWV change between salt-sensitive vs. salt-resistant subjects. This is a between-groups comparison based on a two-sample t test and two-sided Type I error of 5%.

The remainder of the outcomes are *Phase 2*-related, i.e. intended to determine longer-term effects of dietary change between the WHEELS and non-WHEELS groups, with both receiving motivational interviewing-based dietary counseling. The primary outcome of *Phase 2* was the change in left ventricular mass index (LVMI, using the Devereaux and Dubois formulas for left ventricular mass and body surface area, respectively) by echocardiography, with secondary outcome of change in PWV, between baseline and end of study participation. These outcomes were assessed using linear regression adjusted for baseline value. Key additional pre-specified outcomes were the change in DASH/SRD adherence measured both by 3-day food diary and Food Frequency Questionnaire (FFQ) and the change in clinic systolic and diastolic blood pressure (BP), between baseline and end of study participation. These were measured using generalized estimating equations to account for repeated within-subject measures over time (baseline/2 weeks and at 1 and 6 months of *Phase 2*) and interaction with WHEELS treatment group assignment. Other pre-specified outcomes were changes in serum triglycerides and urine sodium:potassium ratio between baseline to the end of study, evaluated using 2-sample t-testing.

The sample size for *Phase 2* was set by the participants completing *Phase 1* and influenced by drop-out during the 6 months of the interventions to promote DASH/SRD adoption. We assumed that an additional 10% of subjects will drop out during *Phase 2*, resulting in 90 subjects with evaluable data. The sample size was estimated based on anticipated effects on DASH/SRD adherence, the presumed primary driver of cardiovascular and BP changes in the study. Based on national survey data and our preliminary work, we expected the mean baseline DASH/SRD adherence score by 3-day food diary to be 2.5 ± 1.5 points (scale, 0-9). A sample size of 90 provides >80% power to detect an intra-group change of 0.6 between baseline and the end of study, based on paired t-testing two-sided Type I error of 5%. This sample size provides >80% power to detect a differential between group change in dietary score of 0.9, based on a two-sample t test and two-sided Type I error of 5%.

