Dietary sodium restriction to prevent hypertensive heart disease: one size fits all? Dietary sodium restriction to prevent HTN-associated cardiovascular disease, longstanding conventional wisdom based on its blood pressure (BP) lowering effects, has recently become highly controversial (Oparil 2014). Despite its broad-based recommendation, the potential exists for harm related to neurohormonal activation during sodium restriction. In prominent publications from large cohort studies, low dietary sodium intake has been associated with both increased and decreased long-term cardiovascular mortality (Mozaffarian et al. 2014, Mente et al. 2016). With regard to incident HF, the findings are similarly mixed, and depend on the population studied and the approach used to assess dietary sodium content (Konerman et al. 2016). The methodological challenges in linking sodium intake to cardiovascular disease in cohort studies, including systematic measurement errors in sodium intake, reverse causality, and residual confounding, are well-described (Cobb et al. 2014). The Institute of Medicine recently concluded that the "paucity of evidence... strongly points to the need for further research to better define relationships between sodium intake and [cardiovascular disease] risk... (Institute of Medicine 2013)"

Just as importantly, this epidemiological debate obscures the possibility of individual differences in response to sodium intake. Controlled studies in humans have identified a salt-sensitive blood pressure (BP) phenotype, i.e., persons in whom BP is substantially higher during high- than low-sodium intake, and conversely those with salt-resistant BP, whose BP responses to changes in sodium intake are negligible. Risk factors for the salt-sensitive phenotype include age, HTN, obesity, and the metabolic syndrome. Independent of baseline BP or previously diagnosed HTN, the salt-sensitive BP pattern triples the risk for cardiovascular morbidity and nearly doubles the long-term mortality hazard (Morimoto et al. 1997, Weinberger et al. 2001). The American Heart Association recently affirmed salt-sensitivity as an independent cardiovascular risk factor with important public health implications, and recommended further study of this phenomenon (Elijovich et al. 2016).

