In addition, the ESS value in older women correlated with C-reactive protein, a measure of inflammation ( $\rho$  0.25, p=0.01), the adipokines leptin ( $\rho$  0.23, p=0.003) and resistin ( $\rho$  0.18, p=0.02), and brachial-ankle pulse wave velocity, a measure of arterial stiffness ( $\rho$  0.16, p=0.03). The relationship between ESS and brachial-ankle pulse wave velocity was independent of other predictors of arterial stiffness, including age, black race, body mass index, and the presence or absence of metabolic syndrome ( $\beta$  8.7 cm/s per 10% increase in ESS, p=0.049). Taken together, these data indicate that the ESS, a measure of impaired eGC sodium-buffering capacity, is: a) increased in HFpEF, consistent with our central hypothesis that salt-sensitivity contributes to HFpEF, b) increased but retains substantial variability in persons with expected higher prevalence of salt-sensitivity, and c) significantly associated with several parameters that predict incident HF.

[figure not shown]

Line: median, +: mean, whiskers 5-95%

Efficacy of motivational interviewing to reduce dietary sodium intake: [name] and colleagues recently studied the effects of dietary sodium restriction on 24-hour ambulatory blood pressure and fluid volume as measured by whole-body bioimpedance in 35 patients with chronic kidney disease (age 60±12 years, 62% male, body mass index 33±5 kg/m², 95% hypertensive). The 4-week dietary intervention aimed to reduce sodium intake below 85 mmol (1955 mg)/day. The protocol involved four in-person contacts with a research dietitian, who used motivational interviewing techniques to lessen the subject's resistance to change dietary behavior and empower them to make lower sodium food choices (Miller et al. 2012). The intervention significantly reduced (all p<0.001) mean 24-hour urinary sodium excretion (by 46%, 170±40 to 92±39 mmol/24h), 24-hour systolic BP (143±22 to 125±19 mmHg) and total extracellular volume (-1.5 liters compared to baseline). These data show that motivational interviewing can reduce short-term sodium intake, promoting beneficial cardiovascular changes in obese hypertensives with chronic kidney disease.

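### The SAP's Phase 1 primary compares non-randomised salt-sensitivity groups adjusted only for baseline; the protocol's further confounders are dropped without explanation, leaving the contrast open to confounding

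*SAP*

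**What the plan says.** SAP, *Statistical Plan*, Phase 1 paragraphs: because Phase 1 came before randomisation, "the comparator groups are salt-sensitive and non salt-sensitive individuals". The primary outcome is the change in PWV from week 2 to week 4, and the change in left ventricular global longitudinal strain is secondary. Phase 1 "outcomes were analyzed using linear regression adjusted for baseline value", and no other covariate is named. Salt-sensitivity is "defined as a reduction in mean arterial pressure by 24-hour ambulatory monitoring in week 4" relative to week 2, with no threshold. The protocol (*Phase 1 study design*) used a "change in 24-hour mean BP of ≥8 mmHg between control and DASH/SRD dietary segments".

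Protocol, Section D, Study phase 1, *Analysis plan*: the effect of diet on cfPWV is estimated in a linear mixed model, "adjusting for baseline cfPWV and other potential confounders, e.g. age, race, body mass index, diabetes status, and renal function". For the phenotype question, "interaction will be assessed via the linear mixed model described above, with a fixed-effect term for salt-sensitivity phenotype".

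Two other places in the protocol bear on which covariates matter:

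- *Background and Significance*, on dietary sodium restriction: "Risk factors for the salt-sensitive phenotype include age, HTN, obesity, and the metabolic syndrome".
- *Preliminary Data*: the relation of the erythrocyte salt-sensitivity test to brachial-ankle PWV is reported as "independent of other predictors of arterial stiffness, including age, black race, body mass index, and the presence or absence of metabolic syndrome".

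The protocol also foresees covariates when participants are compared by phenotype in its Phase 2 and Aim 3 analysis plans, although the Phase 2 ones are different variables (dietary concordance and BP change).

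**The concern.** The protocol's Phase 1 primary was a diet comparison within the same person, where the main effects of fixed traits largely cancel. The SAP's contrast is between different people, where they do not. So the analysis moved to a comparison that is more exposed to confounding, and at the same point the covariates beyond baseline disappeared without comment.

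Adjusting for baseline PWV deals with the measured starting level. It does not deal with any dependence of the two-week change on age, body size, diabetes or renal function at a given starting level. If salt-sensitive participants are, say, older or heavier, and such people respond differently to two weeks of DASH/SRD, the regression would credit that difference to the phenotype. The protocol's hypothesis is that salt-sensitive veterans improve more, so readers are likely to take a group difference as a property of salt-sensitivity.

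**Working it through.** **1. The plan's own figure.** For the phenotype contrast the SAP states more than 80% power at an effect size of 0.5 (100 participants, two-sample t test, two-sided 5%). With 50 per group the noncentrality is 0.5 / √(1/50 + 1/50) = 0.5 / 0.2 = 2.5, and power is 0.697. The stated figure does not reproduce on this reading:

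- A one-sided 5% test gives 0.80, but the text says two-sided.
- Taking 0.5 in units of the raw SD, with the stated correlation of 0.70, gives 0.5 / √(2 × 0.30) = 0.5 / 0.775 = 0.645 and power 0.89. The protocol's 70:30 figure of 0.62, however, reproduces (0.617) only in units of the SD of change.

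I use the SD of change below. The present point does not depend on the power claim. The value 0.697 is only the reference for the cost of adjustment.

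**2. What the documents supply on confounding.** A confounder here needs a link to the group and a link to PWV change at a given baseline.

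- *Link to group:* age and obesity are named. Hypertension and metabolic syndrome are named too, but they are entry criteria, so their presence cannot differ between groups. Race, diabetes and renal function are not named.
- *Link to outcome:* age, race, BMI and metabolic syndrome are named as predictors of the level of stiffness (brachial-ankle PWV in older women). None is linked to two-week change in cfPWV. A level link is not irrelevant: with an assumed within-subject correlation of 0.70, one baseline reading does not capture all of a person's stiffness level, so a predictor of level may still predict change at a given baseline. The documents do not show that it does.
- *Imbalance between groups:* not reported.

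**3. Size under assumed inputs.** Bias from one omitted covariate = D × b. D is the group difference in the covariate (in SD, at a given baseline) and b is the slope of PWV change on it (SD of change per SD of covariate). Both are assumptions. With 50 per group, noncentrality = bias / 0.2. The rejection rate of a two-sided 5% test with no true phenotype difference uses the noncentral t with 97 degrees of freedom. Example: D = 0.5 and b = 0.2 give bias 0.10, noncentrality 0.5 and rejection 7.9%.

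| D | b = 0.1 | b = 0.2 | b = 0.3 |
|---|---|---|---|
| 0.2 | 0.02; 5.1% | 0.04; 5.5% | 0.06; 6.0% |
| 0.5 | 0.05; 5.7% | 0.10; 7.9% | 0.15; 11.5% |
| 0.8 | 0.08; 6.8% | 0.16; 12.4% | 0.24; 22.1% |

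(Each cell: bias in SD of change; type I error.) Against the design effect of 0.5, the bias runs from 0.02/0.5 = 4% to 0.24/0.5 = 48%.

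**4. Cost of adjusting.** With baseline, group and five further terms, df = 100 − 2 − 1 − 5 = 92 and noncentrality = 0.5 / √[(1 − R²) × V × (1/50 + 1/50)]. R² is the share of variance the added covariates explain, and V is the variance inflation from their correlation with group.

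- R² = 0, V = 1 (lost degrees of freedom only): 0.696, against 0.697.
- R² = 0, V = 1.25: 0.60.
- R² = 0.2, V = 1: 0.79.

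**The case against.** Several points on the other side stand.

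- A reader might infer that the SAP removed a fixed covariate list. The documents do not support that. The five covariates are introduced as examples, they are attached to the diet model, and they reach the phenotype test only because that test refers back to the same model.
- A reader might infer that the SAP took away a protection the protocol gave the phenotype contrast. As written, the protocol names no covariate-by-diet terms. With complete data from two periods, a fixed covariate's main effect cancels in each participant's difference and so does not move a diet-by-phenotype interaction. It can move the SAP's baseline-adjusted regression of change. That is a reason to run the adjusted model, not evidence of lost protection.
- A reader might infer that the contrast is in fact confounded. No imbalance is reported, and no covariate is tied to change given baseline. Eligibility also narrows the room for imbalance: everyone has hypertension and meets a BMI or waist criterion, and eGFR below 45 and HbA1c above 10% are excluded.
- If the phenotype is meant only as a marker of who responds, a contrast adjusted for baseline alone is a valid description.
- The SAP is dated May 2025 and written in the past tense. Swapping in a new primary model now would add analytic flexibility.

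What remains is that the protocol committed to adjusting for potential confounders beyond baseline, that the SAP's contrast is the one where this matters more, and that the SAP neither names any nor says why. A non-randomised contrast does not need proven imbalance before an adjusted analysis is worth reporting.

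**Conclusion.** The point holds as an unexplained difference between protocol and SAP that leaves the Phase 1 primary open to confounding. The documents do not show that the contrast is confounded, and they do not allow the size to be computed. The range of 0.02 to 0.24 SD, with type I error of about 5% to 22%, rests entirely on the assumed imbalance and slope, on a single omitted covariate, and on a 50:50 split. The protocol expects 30–50% of participants to be salt-sensitive, and the SAP's definition without a threshold makes the split less certain still.

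Adjustment would not make the comparison clean. The groups are defined by BP change over the same week 2 to week 4 interval as the PWV change, so any correlation between the two changes produces a group gap by itself. The five covariates do not address that separate problem.

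**What to change.** Report two regressions side by side for PWV change, and likewise for strain change: the SAP's model adjusted for the Week 2 value only, and the same model with age, race, BMI, diabetes status and eGFR added, all taken before the DASH/SRD period. State which of the two follows the protocol's covariate intention (neither is its mixed model) and why the SAP departed from it. The adjusted model should not silently replace the reported one. If the two disagree, limit the conclusion to a description of who responded and do not attribute the difference to salt-sensitivity itself.

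The cost is one added SAP paragraph and about five degrees of freedom, or slightly more if race or diabetes needs several categories. Power at an effect of 0.5 would lie at about 0.60 to 0.79, against 0.697, under the assumed R² of 0 to 0.2 and variance inflation of 1 to 1.25. BMI, renal and diabetes data come from the screening measurements and blood tests. The procedure table does not list age and race, but the protocol already planned to use them.
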